Data on these occurrences will be collected on the participant CRF, and documented on an incident log (appendix 3) during each session. This information will be periodically assessed a member of the research team to identify any further training needs for the rehabilitation specialists.

Patients who are identified to have any suicidal thoughts (according to the PHQ-9 questionnaire at baseline) will be managed according to standard clinical practice in Georgia e.g. referral to a psychologist or primary care doctor.

Serious adverse events

Serious adverse events (SAEs) will be defined as an untoward medical occurrence that results in death, is life-threatening, requires hospitalisation, results in persistent or significant disability or incapacity, or is considered medically significant by the study investigator.

There are some potential SAEs which could be expected to occur during the exercise components of the PR programme, although assessing the eligibility of the participants according to the exclusion criteria will minimise this risk e.g. people with unstable cardiovascular disease, musculoskeletal or neurological conditions the prevent exercise and those with very poor balance.

We do not anticipate SAEs to occur in this study, but this is a group of patients with comorbidities doing an exercise intervention. With suitable monitoring by the rehabilitation specialists, we would expect SAEs to be minimised. But if they do occur, all SAEs will be recorded in the CRF and the database. SAEs will be reported to the chief investigator immediately and within 2 working days of being made aware of the event. If, in the opinion of the local doctor or chief investigator, the event was: 'related' (resulted from the administration of any of the research procedures) and 'unexpected'

(not in our list of expected events), and also occurred within 24h of the study assessment, these will be reported to the lead and local in-country ethics committees, sponsor, UoB team and UoB ethics committee (appendix 4).

Auditing

The study may be subject to inspection and audit by the Chapidze Emergency Cardiology Center, under their remit as sponsor, and other regulatory bodies, to ensure adherence to agreed and relevant principles of GCP and local regulatory frameworks.

Research sites will receive study-specific training before recruitment commences, and all sites will be monitored by the research team throughout the study period.

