In-patient hospitalisation of existing hospitalisation Persistent or significant				Cause of death: Initial Prolonged Date of	
In-patient hospitalisation of existing hospitalisation Persistent or significant disability/incapacity				Cause of death: Initial Prolonged Date of	D D M M Y Y Y Y D D M M Y Y Y Y
In-patient hospitalisation of existing hospitalisation Persistent or significant				Cause of death: Initial Prolonged Date of	

Date of Onset	D D M M	Y Y Y Y	Date became serious	D D M M Y Y Y
Date aware	D D M M	Y Y Y Y	Date resolved	D D M M Y Y Y Y
			or tick if ongoing	
	Causality Assse	ssment (perfo	rmed by Medica	al Doctor)
Is the event directly relat	ed, or caused			
by participation in this stu	udy?			
Yes No No				
Person reporting				
Name				Date reported
Signature of Lead Doctor medically qualified delega				D D M M Y Y Y
 Send this even Enter this fo 	([name] or Ta	within 2 workin [name]	_
NAME OF PERSON ENTERIN	IG THIS FORM ON 1	THE DATABASE:		
DATE FORM WAS ENTERED	D D M M	Y Y Y Y]	

Part 2:

To be completed by the Main Coordinating

Centre Chief Investigator

On receipt of an SAE Form, a unique SAE number will be issued. The CI or delegate will independently determine the seriousness, relatedness and the expectedness of the SAE. An SAE judged by the PI, CI or delegate to have a reasonable causal relationship with the study will be regarded as a related SAE. The causality assessment given by the PI will not be downgraded by the CI or delegate. If the CI or delegate disagrees with the PI's causality assessment, the opinion of both parties will be documented, and where the event requires further reporting, the opinion will be provided with the report to Local and UoB Ethics Committees, the Sponsor and the UoB Breathe Well Team, within 15 days of receipt.

Initial Report

Unique SAE number

Review of relatedness to the study by Chief Investigator or delegate

Relateness to study

If the event is related, fill in the Expectedness section, below.

If the event is not related, do not do not assess expectedness, and do not report the event.

Signature of CI or delegate

Is the event expected, according to the protocol?

Expected

See list at end of this form

Related

Date of CI or delegate signature

Unrelated

If event is related and unexpected, please report it to:

Name of Chief Investigator

or delegate

1) Local Ethics 2) UoB team 3) The Sponsor

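### The Appendix 4 SAE form omits the UoB ethics committee from its recipients, and its wording permits a relatedness downgrade by the chief investigator alone that its own introduction forbids

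*Protocol*

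**What the plan says.** Three places in the Protocol govern how a serious adverse event leaves the trial team.

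**Main text (Methods: Monitoring, Harms, Serious adverse events).** External reporting depends on the view of either clinician: "If, in the opinion of the local doctor or chief investigator, the event was" related and unexpected. A further condition is that the event fell within 24 hours of the study assessment. The recipients follow, with a pointer to the form: "these will be reported to the lead and local in-country ethics committees, sponsor, UoB team and UoB ethics committee (appendix 4".

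**Appendix 4, Part 2, introduction.** This applies the same either-party rule: "An SAE judged by the PI, CI or delegate to have a reasonable causal relationship with the study will be regarded as a related SAE". It adds: "The causality assessment given by the PI will not be downgraded by the CI or delegate". Where the two assessors differ, both views are documented and, if further reporting is needed, supplied "with the report to Local and UoB Ethics Committees, the Sponsor and the UoB Breathe Well Team, within 15 days of receipt".

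**Appendix 4, Part 2, action box and what follows it.** The box is headed "Review of relatedness to the study by Chief Investigator or delegate". For an event that is not related the instruction is "do not assess expectedness, and do not report the event". For an event that is both related and unexpected, the addressees are "1) Local Ethics 2) UoB team 3) The Sponsor". The date fields after the box cover the same three. The expectedness table at the end of the form mentions ethics without saying which committee, together with the sponsor and the UoB team.

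**The concern.** The main text refers to Appendix 4 for this reporting, and the Protocol describes no other route for external SAE reports. Staff handling an event will work from the box and its date fields, so what those say matters more in practice than the paragraph above them.

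Two things could go wrong. A reportable event could be sent to every addressee on the form and still not reach the UoB ethics committee, which the main text and the introduction both name. And where the site doctor thinks the event related and the chief investigator does not, the box can be completed so that expectedness is never judged and nothing is sent. That disagreement is the case the no-downgrade rule exists to protect.

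**Working it through.** No arithmetic applies, so the check sets the texts side by side. The main text speaks of the local doctor, the introduction of the PI, and Part 1 of the site's medical doctor. I take these to be the same site assessor.

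**Recipients**

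| Recipient | Main text | Part 2 introduction | Part 2 box | Date fields |
|---|---|---|---|---|
| Local ethics committee | yes | yes | yes | yes |
| UoB ethics committee | yes | yes | no | no |
| Lead ethics committee | yes | not named | not named | not named |
| Sponsor | yes | yes | yes | yes |
| UoB team | yes | yes | yes | yes |

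The UoB ethics committee is in both governing texts and in neither working part of the form. Because the three-name list occurs twice, in the box and again in the date fields, a lost line of layout is an unlikely explanation. The lead committee is less clear. The main text names it beside the local one, but the section on research ethics approval mentions a single application, to the sponsoring centre, so the Protocol does not settle whether the two are distinct.

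**Relatedness**

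Take an unexpected SAE within the 24-hour window and compare the outcome under the either-party rule with the outcome if the box is completed on the chief investigator's view, as its heading suggests.

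| Site doctor | Chief investigator or delegate | Main text and introduction | Box, on the chief investigator's view |
|---|---|---|---|
| related | related | report | report |
| related | unrelated | report | stop, no report |
| unrelated | related | report | report |
| unrelated | unrelated | no report | no report |

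The outcomes differ in one row of four.

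Three features make that reading of the box a natural one. Its heading assigns the review to the chief investigator or delegate. The introduction tells that person to reach an independent view of relatedness. And the box does not refer back to the causality answer in Part 1.

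The 24-hour condition stands in the main text and not in the form. Outside that window a disputed event is not reportable under the main text, so the second row is a conflict with the main text only for events inside it. The conflict with the introduction does not depend on the window.

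**The case against.** The strongest reply concerns relatedness. The box speaks of the event being not related, not of the chief investigator judging it so. The introduction just above defines a related SAE as one that any of the assessors considers related, forbids downgrading and provides for disagreement. Read through that definition, an event the site marks as related goes on to the expectedness section and there is no contradiction. The chief investigator also has the site's answer to hand, because Part 1 is sent to the coordinating office before Part 2 is filled in. This reading is available, and it reduces the point from a contradiction to wording that permits the wrong outcome. It does not remove the point, because the box nowhere says that its term carries the introduction's meaning and its heading points the other way.

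On recipients the reply is weaker. The UoB team might forward reports to its own ethics committee, but no text says so and no field would record it.

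A reader might infer more than the Protocol supports:

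- That the form gives the chief investigator an outright veto, so that every disputed SAE goes unreported. This assumes the introduction is ignored each time.
- That every disputed, unexpected event would otherwise be reportable. This overlooks the 24-hour condition in the main text.
- That events would be lost to the trial. The main text has all SAEs recorded in the CRF and the database, so the possible loss is in external reporting, not in data capture.
- That the trial's purpose of showing safe delivery is undermined. Neither the objectives nor the listed feasibility outcomes include safety, and only certain non-serious events are said to form part of the study outcomes.

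**Conclusion.** The point holds in two parts of unequal strength. The recipient mismatch needs no interpretation: a report made from the form as written goes to three addressees and leaves out the UoB ethics committee, which both governing texts require. The lead committee is also not separately named, which matters only if it is distinct from the local one. The relatedness part is a defect of wording: the box allows a one-person downgrade in the single case of site related and chief investigator unrelated, although the same page rules it out.

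The number of events concerned cannot be derived from the Protocol. It gives no SAE rate and does not anticipate SAEs, so with 60 participants the number is probably small. Nothing here touches the sample size or the analysis. The case for correcting the form is that it governs oversight and the repair is nearly free.

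**What to change.** Reconcile the main text, the Part 2 introduction and the working parts of the form.

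1. Make the box's recipient list and the date fields match the main text: add the UoB ethics committee with its own date field, and the lead committee if it is distinct from the local one. Have the expectedness table name the committees it means.
2. Reword the box along these lines: *Stop here only if both the site doctor (Part 1) and the chief investigator or delegate consider the event unrelated. If either considers it related, complete the expectedness section; where a report is due and the two differ, send both opinions.*
3. Carry the site doctor's Part 1 answer into Part 2 as a printed field, so that a disagreement is visible where the decision is made.
4. State in both places, or in neither, whether the 24-hour condition applies.

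The cost is a few words and two or three fields on one form. The downside is possibly a few more external reports.
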